15.2 Other endpoints

15.2.1 Laboratory parameters

The following laboratory parameters will be analyzed as continuous variables:

Hematology panel	
Hemoglobin	Red blood cell (RBC) count
Hematocrit	Red blood cell morphology
Mean cell volume (MCV)	White blood cell (WBC) count
White blood cell morphology	White blood cell differential count
Platelet count	

Clinical chemistry panel

Sodium	Lipase
Potassium	Triglycerides
Chloride	Total serum bilirubin
Blood urea nitrogen (BUN)	Alkaline phosphatase
Creatinine	Creatine phosphokinase
Uric acid	Lactic acid dehydrogenase (LDH)
Calcium	Alanine transaminase (ALT)
Phosphorus	Aspartate transaminase (AST)
Albumin	Gamma-glutamyltransferase (GGT)
Total protein	Glucose

Urine dipstick by the local laboratory

pH	Specific gravity
----	------------------

The following categorical laboratory parameters will be summarized:

Urine dipstick by the local laboratory

Glucose	Bilirubin
Protein	Urobilinogen
Blood	Nitrite
Ketones	Leukocyte esterase

Parameters of the Hematology and clinical chemistry panel are assessed by a central laboratory and for a subset of parameters additionally at baseline of Part 1 by a local laboratory. For summary statistics and for the classification of values based on the reference and alert ranges, only values obtained from the central laboratory will be used. The creatinine clearance (CL_{CR}) will be calculated in the eCRF using a central laboratory standard age appropriate formula and will also be analyzed. Dipstick urinalysis will be performed locally and will be used for summary statistics. Only in case of abnormalities, a urine sample will be sent to the central laboratory for sediment analysis. These results will only be included in the subject data listings.

Laboratory data will be descriptively summarized by type of laboratory test and by visit. Change from Baseline to each visit will be presented for all laboratory parameters.

Shift tables from baseline for the different visits and overall post-baseline (see Section 18.1.12.1) will be generated for each laboratory parameter for categories low, normal and high, based on the reference ranges of the central laboratory.

Furthermore, a summary by type of laboratory test, by visit and overall post-baseline will be provided on the number and percentage of subjects with a value outside the sponsor defined alert ranges (potentially clinically important (PCI) values, Section 18.2). See Section 18.1.12 for details regarding the analysis.

For the Tapentadol Period of Part 2, graphical presentations over time of the trial for the observed data will be provided (mean and 95% confidence interval), including numbers on the top and the bottom of the plot representing the number of subjects and the frequency of subjects with a PCI value by visit for the two arms of differently pretreated subjects.

These graphs will be provided for the continuous laboratory parameters given in [Table 6](#).

Table 6: Laboratory parameters presented in graphical illustrations

Lactic acid dehydrogenase (LDH)	Alanine transaminase (ALT)	Aspartate transaminase (AST)
Gamma glutamyltransferase (GGT)	Alkaline phosphatase	Total serum bilirubin

A listing of subjects with PCI values will be provided. A listing of subjects with any laboratory results outside the reference ranges will be provided.

Subjects potentially qualifying for Hy's law criteria (FDA 2009), i.e., subjects showing confirmed (repeated) post-randomization (including unscheduled visits) values of ALT or AST of >3 x ULN and total bilirubin of >2 x ULN, will be given in a separate listing.

All laboratory values will be presented in the subject data listing of the respective part. Values out of reference ranges will be flagged as H (above the reference range) or L (below the reference range) in the listing. If a value classified as high or low is in addition also out of alert ranges, it will be flagged as H* or L* in the listing.

15.2.2 **Electrocardiogram**

Twelve-lead electrocardiogram parameters are RR interval, PR interval, QRS interval, QT interval and heart rate and are assessed during Part 1 only. Furthermore, the QTcF interval will be calculated using Fridericia ($QTcF = QT / (RR)^{1/2}$) correction. The investigator will record clinically relevant abnormalities and their medical interpretation in the eCRF. Cardiologists at a central ECG laboratory will read all ECGs. The ECG report from the central ECG laboratory will be considered a source document.

Electrocardiogram parameters will be summarized by visit. Changes from baseline to Visit VE will be presented descriptively.

Shift tables from baseline to Visit VE and overall (worst value on treatment, see [Section 18.1.12.1](#) for definition of worst) will be generated for each ECG parameter for categories low, normal and high, based on the reference ranges provided in [Table 7](#) and for categories normal, prolonged regarding the QTcF based on reference ranges provided in [Table 8](#). Furthermore for the overall interpretation on ECG findings ('normal', 'abnormal, clinically not relevant' and 'abnormal, clinically relevant') assessed by the investigator, a summary by visit and overall post-baseline will be provided. See [Section 18.1.12.1](#) for details regarding the analysis. A subject data listing of all abnormal, clinically relevant findings as documented by the investigator in the eCRF will be created.

All ECG values will be presented in the subject data listing. Values out of reference ranges (based on [Table 7](#) and [Table 8](#)) will be flagged as H (above the reference range) or L (below the reference range) in the listing.

In case of the occurrence of a clear technical problem, the non-reliable measurements will be ignored during the analysis but will be shown in the subject data listings.

Table 7: Classification of abnormal ECG parameters

Parameter (unit)	Age class	Abnormally low	Abnormally high
PR (msec)	6 - < 12 years	<100	>180
	12 - <18 years	<100	>200
QRS (msec)	6 - <12 years	<50	>89
	12 - <18 years	<60	>99
QT (msec)	6 - <18 years	<320	>450
RR (msec)	6 - <18 years	<600	>1200

The ECG parameters are based on standard criteria of the ECG provider ERT.

Table 8: Classification of abnormal QTcF values

Parameter (unit)	Classification	Criterion
QTcF_MN (msec)	Normal	≤ 450
	Prolonged	>450

The QTcF_MN (_MN: mean of all beats) values are based on standard criteria of the ECG provider ERT.

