1.3.2 Exclusion criteria

Subjects are not eligible for the trial if any of the following apply:

The following will be checked at Visit V1:

Exclusion criteria	Rationale for criterion
1. Has been previously enrolled in this trial or a previous trial with tapentadol.	Ethics and interference with trial assessments.
2. Has a clinically relevant history of hypersensitivity, allergy, or contraindication to morphine or tapentadol or any ingredient, including galactose intolerance (see investigator's brochure for tapentadol PR and summary of product characteristics for morphine PR), or naloxone.	Safety.
3. History or current condition of any one of the following: 
 Seizure disorder or epilepsy. Serotonin syndrome. Traumatic or hypoxic brain injury, brain contusion, stroke, transient ischemic attack, intracranial hematoma, posttraumatic amnesia, brain neoplasm, or episode(s) of more than 24 hours duration of unconsciousness. 	Safety and interference with trial assessments.
4. History or current condition of any one of the following: 
 Moderate to severe renal or hepatic impairment. Abnormal pulmonary function or clinically relevant respiratory disease (e.g., acute or severe bronchial asthma, hypercapnia). Complex regional pain syndrome. A pain indication with a strong psycho-somatic component that, in the judgment of the investigator, is unlikely to respond to opioids. 	Safety and interference with trial assessments.
5. History of alcohol or drug abuse in the investigator's judgment, based on history and physical examination. Drugs of abuse detected in urine screen unless explained by allowed concomitant medication (see synopsis section Concomitant medications/therapies).	Safety.
6. Subject has: 
 A clinically relevant abnormal ECG. Signs of pre-excitation syndrome. Brugada's syndrome. QT or QTcF (Fridericia) interval >470 ms. 	Safety.
7. Any surgery scheduled during Part 1 of the trial that is expected to require post-surgical intensive care unit (ICU) treatment, or that	Safety.

Confidential

Protocol KF5503-66
including Amendment 05

Page 21 of 137
DMS version 9.0
27 Jul 2017

Exclusion criteria	Rationale for criterion
requires post-surgical parenteral pain-treatment, or may, in the opinion of the investigator, affect the safety of the subject.	

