14.2.7.3 Electrocardiogram

The ECG variables that will be analyzed are heart rate, RR interval, PR interval, QRS interval, QT interval, and QTcF (Fridericia) interval.

The ECG measurements will be summarized at each time point of measurement during the treatment period. The change from baseline will also be summarized. A categorical analysis for outliers will be performed as per the guidance “Clinical evaluation of QT/QTc interval prolongation and proarrhythmic potential for non-antiarrhythmic drugs” (ICH Topic E14).

All important abnormalities from the ECG readings, including changes in general and changes in T wave morphology, or the occurrence of U waves versus baseline recordings, will be reported.

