7 DOCUMENT AND CHANGE HISTORY

7.1 Changes in analysis compared to the trial protocol

Not applicable.

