15 SAFETY ANALYSES

No statistical tests for comparison of safety data between treatment arms will be performed.

Safety data will be summarized descriptively as described in Section [8.1](#).

All safety data will be presented for the SAF unless otherwise specified.

Unless otherwise specified, separate descriptive analyses will be performed for the different trial periods and respective treatment groups.

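### SAP 15.2.2 names the Fridericia correction but prints the square-root (Bazett) formula for QTcF and gives no RR unit

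*SAP*

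**What the plan says.** SAP 15.2.2 (Electrocardiogram) gives method and formula in one sentence. It opens "Furthermore, the QTcF interval will be calculated using Fridericia" and then, in brackets, sets QTcF equal to QT / (RR)^(1/2). It attaches no unit to RR.

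The other places that bear on the point are:

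- **Protocol 14.2.7.3** lists the variables to be analysed, ending with "QT interval, and QTcF (Fridericia) interval". It gives no formula and also commits to a categorical outlier analysis following ICH E14.
- **Protocol 1.3.2, exclusion criterion 6**, uses the same correction: "QT or QTcF (Fridericia) interval >470 ms".
- **SAP Table 7** gives RR in msec, abnormal below 600 or above 1200.
- **SAP Table 8** classes a variable called QTcF_MN, described as a mean over all beats, as normal up to 450 msec and prolonged above. Its footnote says that the "values are based on standard criteria of the ECG provider ERT".
- **SAP 7.1**, headed "Changes in analysis compared to the trial protocol", is marked as not applicable.
- **SAP 18.1.12**, the programming section covering ECG parameters, contains no QTc formula.

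**The concern.** The method named and the formula printed are different corrections. Since SAP 7.1 declares no departure from the protocol, the square root cannot be read as a deliberate change. Nothing elsewhere in the SAP or its amendment logs corrects it, so it is the only QTc expression a programmer has.

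The missing unit makes the mistake harder to catch. With RR in msec the printed formula gives absurdly small values that someone would notice. The natural repair is to convert RR to seconds and keep the exponent. That gives plausible numbers under the label QTcF that are not Fridericia values.

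The outputs at stake are the Part 1 QTcF summaries, the changes from baseline to Visit VE, the normal/prolonged shift tables, the flags in the listings, and any QTc outlier table. A shift in heart rate between Visits V1 and VE would also appear as a QTcF change when there was none.

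**Working it through.** **Inputs.** Printed exponent 1/2 (SAP 15.2.2). Named method Fridericia (SAP 15.2.2; protocol 14.2.7.3). Normal heart rates by age (SAP Table 9). RR limits 600 and 1200 msec (SAP Table 7). Prolonged above 450 msec (SAP Table 8). One input is not in the documents: a reference QTcF, assumed to be 400–420 ms.

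**Formulas**, with RR = 60/HR in seconds:

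- Fridericia: QT / RR^(1/3)
- As printed: QT / RR^(1/2)
- Ratio, printed to Fridericia: RR^(−1/6) = (HR/60)^(1/6)
- Error in ms: QTcF × (ratio − 1)

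The ratio is 1 at 60 bpm, above 1 at faster rates and below 1 at slower ones. No choice of RR unit turns an exponent of 1/2 into Fridericia.

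**Error at the low, middle and high end of each Table 9 range, for a true QTcF of 400–420 ms:**

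| Age (years) | HR, bpm | Ratio, low / high | Error low / middle / high, ms |
|---|---|---|---|
| 6–<9 | 74–111 | 1.0356 / 1.1080 | +14 to +15 / +30 to +31 / +43 to +45 |
| 9–<12 | 67–103 | 1.0186 / 1.0942 | +7 to +8 / +24 to +25 / +38 to +40 |
| 12–<16 | 62–96 | 1.0055 / 1.0815 | +2 / +19 to +20 / +33 to +34 |
| 16–<18 | 58–92 | 0.9944 / 1.0738 | −2 / +15 to +16 / +30 to +31 |

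For example, at 111 bpm: 400 × 0.1080 = 43.2 ms and 420 × 0.1080 ≈ 45.3 ms.

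**At the Table 7 limits.** RR 600 msec is 100 bpm, ratio 1.0889, error +36 to +37 ms. RR 1200 msec is 50 bpm, ratio 0.9701, error −12 to −13 ms.

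**Sensitivity to the assumed QTcF.** From 380 to 450 ms, the low end (58 bpm) moves from −2.1 to −2.5 ms and the high end (111 bpm) from +41.0 to +48.6 ms.

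**Effect on the Table 8 classes.** The printed value reaches 450 when the true Fridericia value is 450/ratio:

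- 111 bpm: 450/1.1080 = 406.1 ms
- 100 bpm: 450/1.0889 = 413.3 ms
- 92 bpm: 450/1.0738 = 419.1 ms
- 74 bpm: 450/1.0356 = 434.5 ms
- 50 bpm: 450/0.9701 = 463.9 ms

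At the first four rates, true values between the figure shown and 450 ms would be called prolonged. At 50 bpm, true values from 450 to about 464 ms would be called normal. As a single case, QT 340 ms at 111 bpm is 417.4 ms by Fridericia (normal) and 462.4 ms as printed (prolonged).

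**Heart-rate change mistaken for QTcF change.** With true QTcF unchanged, a rise of 10 bpm from 80 or 90 bpm would show as about +8 to +9 ms.

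**RR in msec.** QT 360 with RR 750 gives 360/750^(1/2) = 13.1, which would be noticed.

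**The case against.** The strongest objections concern certainty and reach, not the algebra.

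1. **The exponent is one small superscript.** It was read from text extracted from the PDF, where 1/3 and 1/2 are easily confused, and the formula appears nowhere else for comparison. This stands as a condition: check the PDF page first. If it shows 1/3, only the missing RR unit and the unclear source of QTcF remain.
2. **The intent is plain.** Fridericia is named in both documents and Bazett in neither, so a careful programmer might follow the name. That may be so, but a plan should not depend on the programmer overriding its only formula.
3. **The formula may never be run.** A central laboratory reads all ECGs, and QTcF_MN looks like a variable the provider delivers. Against that, SAP 15.2.2 says QTcF will be calculated, protocol 12.6.4 lists only RR, PR, QRS, QT and heart rate as measured, and the Table 8 footnote speaks of criteria without saying where the values come from. The question is open, and the SAP should settle it.
4. **The +45 ms is the extreme case.** It needs 111 bpm, the upper normal limit of the youngest group, and an assumed QTcF. This is fair: the mid-range errors are about +15 to +31 ms.
5. **The consequence is limited.** ECGs are analysed in Part 1 only, and SAP 15 says: "No statistical tests for comparison of safety data between treatment arms will be performed". This is correct and bounds how serious the point is.

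**Conclusion.** The concern holds. As written, SAP 15.2.2 pairs the Fridericia name with the Bazett formula, and nothing in either document resolves the conflict. If the formula is programmed as printed with RR in seconds, QTcF is off by the factor (HR/60)^(1/6). That is about −2 to +45 ms across the Table 9 normal heart rates, with mid-range errors of about +15 to +31 ms.

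These sizes rest on three conditions: the exponent on the PDF page is indeed 1/2, QTcF is derived from this formula and not taken from the provider, and the true QTcF is 400–420 ms. The ratio itself needs no assumption about QTcF.

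The effect is confined to descriptive Part 1 ECG output. The primary endpoint is untouched. So are the ECG eligibility and discontinuation checks, which under protocol 12.6.4 rest on the investigator and the central ECG report. The point should be fixed before the ECG tables are programmed, but it does not threaten the trial's main conclusion.

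**What to change.** Confirm the exponent on the PDF page of SAP 15.2.2. Then do one of two things:

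- print QTcF = QT/(RR/1000)^(1/3), with QT and RR in msec; or
- state that the Fridericia QTcF_MN supplied by the central ECG provider is used directly, and delete the formula.

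Either way, SAP 15.2.2, Table 8 and protocol 14.2.7.3 should refer to the same quantity. The cost is one line in the SAP. Data collection does not change: QT and RR are recorded, so any QTcF already derived from the printed formula can be recalculated.

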- Confirm whether returned amount of rescue medication matches expected amount to be returned.
- Verify discrepancies with subject, or parent(s), legal guardian(s), or caregiver.

o) Train subject, parent(s), or guardian(s) on tapentadol PR use for subjects entering the Tapentadol Period of Part 2.

Confidential

Protocol KF5503-66
including Amendment 05Page 14 of 137
DMS version 9.0
27 Jul 2017

p) Samples will only be drawn from subjects on tapentadol PR for the determination of serum concentrations of tapentadol and tapentadol-O-glucuronide: 1 sample at Visit V2 (1 hour to 6 hours after IMP intake for out-patients and 3 hours to 6 hours after IMP intake for hospitalized subjects), 1 sample at Visit V3, and 1 sample at Visit VE (at any time during the visit, but after pain assessments).

q) Subjects completing the Treatment Period (Part 1) with tapentadol PR or morphine PR and who have need for continued opioid treatment can enter the Tapentadol Period. Subjects not completing the Treatment Period (Part 1), but who have taken at least 1 dose of IMP, and those who complete the Treatment Period but do not want to continue with tapentadol PR, will enter the Observation Period (12 months). Subjects will be followed until Visit F12M. Subjects in the Tapentadol Period of Part 2 may stop treatment early (before Visit F12M) and switch to Observation period for the remainder of Part 2.

r) Assignment needs to be documented in the case report form and the interactive response technology system.

s) The informed consent/assent may be obtained earlier than Day -14.

t) The inclusion as well as discontinuation of a subject will be based on the judgment of the investigator. If the subject has been included but fulfills any of the discontinuation criteria based on the ECG analysis report of the central ECG laboratory, the ECG must be repeated within 1 week of receiving the central ECG report and the subject must be discontinued if any of the discontinuation criteria is confirmed by the investigator.

Demographic data = date of signing the informed consent/assent form, sex, age, and race/ethnicity; Safety laboratory = hematology, clinical chemistry, and urinalysis; Serum pharmacokinetics = serum concentrations of tapentadol and tapentadol-O-glucuronide; Vital signs = respiratory rate, systolic and diastolic blood pressure, and pulse rate.

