9.3.1 Reasons for discontinuation of a subject from IMP (treatment not completed)

The investigator must discontinue subjects from treatment with IMP (i.e., treatment not completed) for the compulsory reasons (stopping criteria) given in Table 1. For reasons marked as optional, the investigator may decide to stop IMP administration if the benefit/risk ratio for continued administration of IMP is considered not to be favorable.

Table 1: Reasons for compulsory and optional discontinuation of subjects from investigational medicinal product (treatment not completed)

Main reason	Discontinuation from IMP	
	Compulsory	Optional
Adverse event		X
- There is any relevant deterioration in the health of the subject that could alter the benefit/risk assessment for the subject, including adverse events, laboratory parameters, vital signs, or other safety parameters (e.g., ECG).		

Confidential

Protocol KF5503-66
including Amendment 05

Page 48 of 137
DMS version 9.0
27 Jul 2017

Main reason	Discontinuation from IMP	
	Compulsory	Optional

 - A confirmed QT or QTc interval of >470 ms. - Based on data from the central laboratory, clinically relevant change in liver parameters after dosing if the result is confirmed by 1 additional laboratory assessment (see Section 19.7), for 1 or more of: 
 • Alanine transaminase or aspartate transaminase is >5 times above the upper limit of normal. • Alanine transaminase or aspartate transaminase is >3 times above upper limit of normal and total serum bilirubin >2 times above upper limit of normal or international normalized ratio (INR) >1.5 times above the upper limit of normal (without documented pathological screening value or without pharmacological anticoagulation with vitamin K antagonists). 	X	
Death (trial discontinuation)		X
Lack of efficacy		

 - The subject requires more than 4 doses per day of rescue medication on 2 consecutive days for persistent intolerable pain while taking the highest dose of IMP twice daily. 	X	
Pregnancy	X	
Enrollment failure (trial discontinuation)	X	
Protocol deviation		

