18.1.12.1 Overall post-baseline value

For the shift table and PCI frequency table of laboratory, vital signs and ECG parameters, an overall post-baseline value will be derived. Therefore, all post-baseline assessments, including unscheduled assessments, are taken into account.

For the overall post-baseline summary subjects might have both low and high values. These subjects will be categorized in a new category “high and low” and excluded from the categories “high” and “low”. The inclusion of this category in the frequency and shift tables is only required if there are any subjects falling into this category.

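### The SAP does not specify the categorical QT outlier analysis that the protocol promises, and its only QTcF split (450 ms) leaves the trial's own 470 ms limit out of every planned table

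*SAP*

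**What the plan says.** **What the protocol promises.** Protocol 14.2.7.3 names QTcF among the ECG variables and states: "A categorical analysis for outliers will be performed as per the guidance", the guidance being ICH Topic E14. The same section says that important ECG abnormalities, including T-wave changes and new U waves relative to baseline, will be reported.

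**Limits used in the conduct of the trial.** Exclusion criterion 6 (Protocol 1.3.2) includes "QT or QTcF (Fridericia) interval >470 ms". Table 1 in Protocol 9.3.1 lists "A confirmed QT or QTc interval of >470 ms" among the reasons for stopping study medication. Footnote t to the Part 1 schedule (repeated in Protocol 12.6.4) requires a repeat ECG when the central report meets a discontinuation criterion, and adds that "the subject must be discontinued if any of the discontinuation criteria is confirmed by the investigator".

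**What the SAP plans.** SAP 15.2.2 sets up QTcF shift tables from baseline to Visit VE and overall "for categories normal, prolonged regarding the QTcF based on reference ranges provided in" Table 8 ("Table 8: Classification of abnormal QTcF values"). That table has two levels: normal at 450 ms or less, prolonged above 450 ms. The SAP contains no reference to E14, no outlier analysis, no category for change in QTcF, no mention of 470 ms, and no output for T or U waves as such. SAP 7.1, headed "Changes in analysis compared to the trial protocol", is marked as not applicable.

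**Other ECG output in SAP 15.2.2.** Values are summarised by visit and changes from baseline to VE are described. Uncorrected QT has its own shift table, again with 450 ms as the upper limit (Table 7). The investigator's overall ECG interpretation is tabulated in three categories. Clinically relevant abnormal findings are listed. All ECG values are listed, with a flag when outside the reference range.

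**The concern.** The protocol commits to a specific type of safety analysis and leaves the detail to the SAP. The SAP supplies something narrower and does not declare the difference. A reader of the report who relies on the protocol would expect counts of QT outliers by arm. A programmer who relies on the SAP would not produce them.

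The single cut adds to the problem. The trial acts on 470 ms, but its tables recognise only 450 ms. Subjects who begin between these two values cannot be seen to move upward in the shift table, and subjects who begin below 450 ms are pooled once they exceed it, however far they go.

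The scheduled ECGs are at V1 and VE (Protocol 1.2.1), and SAP 15.2.2 confirms that ECG is assessed in Part 1 only. VE is therefore the one scheduled on-treatment ECG, which is a reason to get more from its categorical summary than a split at the reference limit.

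**Working it through.** No sample size, power or error rate is involved. The check applies the SAP's classification rule to pairs of baseline and post-baseline values, then repeats it with one extra band at the protocol's own limit. The values are illustrative and QTcF is taken as given.

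**Inputs**
- SAP Table 8: normal if QTcF is 450 ms or less, prolonged if above 450 ms.
- Protocol 1.3.2: excluded if QT or QTcF is above 470 ms, so this criterion admits a baseline of up to and including 470 ms.
- Protocol 9.3.1: stopping limit above 470 ms, to be confirmed.
- Comparison rule: 450 or less; above 450 to 470; above 470 ms.

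**Result**

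| Baseline → post (ms) | Change | Under SAP Table 8 | With a 470 ms band |
|---|---|---|---|
| 455 → 490 | 490 − 455 = +35 | prolonged → prolonged, no shift | >450–470 → >470, shift |
| 451 → 471 | 471 − 451 = +20 | prolonged → prolonged, no shift | >450–470 → >470, shift |
| 470 → 520 | 520 − 470 = +50 | prolonged → prolonged, no shift | >450–470 → >470, shift |
| 445 → 455 | 455 − 445 = +10 | normal → prolonged | ≤450 → >450–470 |
| 445 → 490 | 490 − 445 = +45 | normal → prolonged | ≤450 → >470 |
| 400 → 449 | 449 − 400 = +49 | normal → normal, no shift | ≤450 → ≤450, no shift |

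Three things follow.

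1. Any baseline above 450 and up to 470 ms, followed by any value above 470 ms, falls in the prolonged-to-prolonged cell (first three rows).
2. For a baseline of 450 ms or less, 455 and 490 ms fall in the same cell (fourth and fifth rows). The table therefore cannot yield the number of subjects above 470 ms, whatever the baseline.
3. The last row shows that a band at 470 ms is not enough by itself: +49 ms below 450 ms is no shift under either rule. Only categories of change from baseline would show it, and the SAP has none.

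**Could another planned table fill the gap?** The uncorrected-QT shift table also stops at 450 ms. The investigator's three-level interpretation is not tied to any QTc value. The descriptive summary of change gives a maximum and quartiles (SAP 8.1), so one large rise shows as an extreme, but not how many subjects rose by how much, nor from where. The listing flag is the same for 451 and 490 ms. For laboratory values and vital signs the SAP provides a second flag beyond alert limits; for ECG it does not. So no planned table gives a count by arm above 470 ms or by size of increase.

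**The case against.** The strongest reply is that this is descriptive safety output in a trial of about 69 subjects with one scheduled post-baseline ECG. Every value is listed and flagged, changes are summarised with their maximum, clinically relevant findings are listed, reasons for stopping study medication are tabulated (SAP 10.2), and adverse events leading to discontinuation are listed (SAP 15.1.2.2). A careful reader can find a value of 490 ms. This stands as a limit on the point. It does not answer it, because a listing and a maximum are not the categorical analysis that the protocol promised.

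A second reply is that a reference limit and a stopping limit serve different purposes and need not coincide. That is fair. The two figures do not contradict each other; the gap is that the second appears in no table.

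Several stronger readings are tempting, and the documents do not support them:

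- *That a child crossing the stopping limit would go unseen, or that the QTcF shift table is the trial's only categorical QT evidence.* The outputs listed above show otherwise.
- *That one QTcF value above 470 ms is a stopping event.* The criterion concerns a confirmed QT or QTc value, with a repeat ECG and the investigator's confirmation. A count above 470 ms is not a count of stopping events.
- *That every subject at 451 to 470 ms is eligible.* The QT limit admits them, but the same exclusion criterion also bars a clinically relevant abnormal ECG.
- *That the protocol requires T-wave and U-wave changes to be tabulated.* It says that they will be reported, which a listing can satisfy. The planned listing of clinically relevant findings may meet part of this.
- *That SAP 18.1.12.1 promises an ECG alert table with no limits.* Its sentence, "For the shift table and PCI frequency table of laboratory, vital signs and ECG parameters, an overall post-baseline value will be derived", is shared wording for three data types, and SAP 15.2.2 plans no such ECG table. The point does not rest on it.

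**Conclusion.** The point holds in this form: the SAP leaves out an analysis that the protocol promises, does not declare the omission, and uses a single QTcF cut that omits the trial's own limit. The consequence is confined to tabulation. A rise from 455 to 490 ms shows as no shift, and no table gives numbers above 470 ms, or by size of increase, for each arm.

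How many subjects this would affect cannot be derived, because the documents give no distribution of baseline QTcF; the number could be zero. The E14 category limits are not reproduced in either document, so the conclusion rests on the missing specification and the missing 470 ms band, not on any particular guideline value. The primary endpoint is untouched. The correction is worth making because it is cheap and because the protocol already commits to the analysis.

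**What to change.** In SAP 15.2.2 and Table 8:

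1. Use three QTcF bands built on the protocol's existing limit (450 or less; above 450 to 470; above 470 ms) in the shift and frequency tables, at VE and overall, by arm.
2. Specify the categorical outlier analysis promised in Protocol 14.2.7.3, including categories for change from baseline, with the category limits taken by reference from the cited guideline.
3. List every subject with a value above 470 ms, stating whether it was confirmed on repeat ECG.
4. Report T-wave and U-wave changes against baseline; a listing is enough.
5. Declare in SAP 7.1, as a deviation from the protocol, any of the promised analysis that will not be done.

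The cost is SAP wording and a small number of tables and listings. Items 1 and 2 use ECG values already collected and centrally read. Item 4 assumes that T-wave and U-wave findings can be obtained from the central reading, since Protocol 12.6.4 names only the intervals and heart rate as measurements. No clinical threshold or management rule changes.
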